6.2.7 Investigational medical device accountability

The IMD must not be used outside the context of this clinical investigation plan (CIP) and the Instructions for Use (IFU). The IMD must be handled in accordance with the Sponsor's instructions (see section 6.2.2 to 6.2.5 and refer to the current version of the IB¹¹ / IFU¹⁶).

Considering the number of subjects to be enrolled, the average volume of the device administered in the clinical investigation of Saypha® FILLER Lidocaine (maximum volume of 2 mL for both lips in total), and potential additional touch-up treatment, when including 110 subjects it is anticipated that up to 440 units (à 1 mL) of the IMD may be used during this clinical investigation.

Documentation of receipt, dispensing/use in individual subjects, and return of IMD must be maintained by the investigator or his/her designee. Appropriate forms will be provided by the Sponsor or their representative to facilitate IMD accountability.

At the end of the clinical investigation, all remaining supplies, including empty boxes of IMD that have been used, must be returned to the Sponsor for accurate destruction and accounting of the IMD.

Empty or used syringes will not be returned to the Sponsor, but will be destroyed by the investigation site, in line with their routine procedure for medical waste disposal. Used needles should be disposed immediately after the use as per routine procedure for medical waste disposal at the site.

According to the underlying monitoring plan (see also section 6.7) the monitor will regularly check study documentation and inventory of IMDs held by the investigator to verify accountability of all devices used.

6.2.8 Handling of deficient investigational medical devices

Any IMD alleged to be deficient must not be used by the investigator and must be returned to the Sponsor. Instructions in section 14.8 must be followed.

6.3 Subjects

6.3.1 Number of subjects and duration of the clinical investigation

Approximately 110 subjects with moderate to severe volume deficiency of lips (defined as grade 1 grade 3 within LFS) will be enrolled and treated with the IMD.

Each subject will participate in the study for up to 18 months. Taking into account the anticipated recruitment period of 2-3 months, the total expected duration of the clinical investigation will be about 21 months.

6.3.2 Recruitment strategy

The recruitment over the study will be competitive and will be stopped as soon as 110 subjects are enrolled in the study.

The study subjects will be recruited by the investigator, among subjects who attend the investigation site seeking the corrective treatment of volume deficiency of their lips.

The investigator may also offer participation in the study to potential candidates identified in their subject database. In case of an unexpectedly low recruitment rate, the investigation may be advertised. In such case, the advertising strategy and materials will be submitted to the Ethics Committee (EC) for prior review and approval.

6.3.3 Inclusion criteria

A subject must meet **ALL** of the following criteria to be **ELIGIBLE** for the study:

- 1. Adult female or male subjects 18 years of age at Screening/Baseline visit (Visit 1)
- 2. Presence of approximately symmetrical "very thin" lips (minimal red lip shows) to "moderately thick" lips (moderate red lip shows) as assessed with the LFS (severity grade of 1 to 3 on both lips) as determined by the investigator at Visit 1
- 3. For females of childbearing potential only: negative urine pregnancy test at Visit 1, and must agree to use an highly effective method of contraception for the duration of the clinical investigation (see section 6.3.7 for details)
- 4. Healthy skin in the treatment area and free of diseases that could interfere in evaluation of treatment
- 5. Willingness to abstain from any cosmetic or surgical procedures in the treatment area for the duration of the clinical investigation
- 6. Willingness to take part in this clinical investigation documented by a personally signed/dated informed consent.

6.3.4 Exclusion criteria

A subject who meets **ANY** of the following criteria is **NOT ELIGIBLE** for the study and must not be enrolled:

- Pregnancy, lactation, planned pregnancy or unwillingness to use contraception at any time during the study (for women of child-bearing potential only) History of mental disorders or emotional instability
- 2. History of allergic reaction or hypersensitivity to hyaluronic acid, lidocaine or any amide-based anaesthetic
- 3. Prior surgery, scars or tattoo to the upper or lower lip or lip line; surgery and tattooing are prohibited until end of clinical investigation
- 4. Tooth gap, overbite, beard longer three-day beard, or excessive facial hair that could interfere in evaluation of treatment as judged by the investigator
- 5. Presence of any abnormal lip structure, such as a scar or lump or severe lip asymmetry, as judged by the investigator
- 6. Previous tissue augmenting therapy in the lip area (including lips, oral commissures, nasolabial folds, marionette and perioral lines) with HA or collagen filler, or laser treatment, chemical peeling, dermabrasion or mesotherapy within 12 months before Visit 1 and until end of clinical investigation
- 7. Previous permanent implant or treatment with non-HA or non-collagen filler in the lip area (including lips, oral commissures, nasolabial folds, marionette and perioral lines) and until end of the investigation
- 8. Previous toxin treatment in the lip area (including lips, oral commissures, nasolabial folds, marionette and perioral lines) within 9 months before Visit 1 and until end of clinical investigation
- 9. Presence of cutaneous lesions, inflammatory and/or infectious processes (e.g. acne, herpes, etc.) or proliferative lesions in the treatment area
- 10. Known human immune deficiency virus-positive individuals
- 11. History of allergies against aesthetic filling products and recurrent (3 times a year) herpes simplex in the treated area
- 12. Tendency to hypertrophic scars, keloid formation and/or pigmentation disorders
- 13. History or presence of any autoimmune or connective tissue disease, or current treatment with immune therapy
- 14. Uncontrolled systemic diseases (such as diabetes mellitus)
- 15. Use of anticoagulant, antiplatelet or thrombolytic medication (e.g. acetylsalicylic acid) from 10 days pre- to three days post IMD injections
- 16. Planned dental/oral surgery or modification (bridge-work, implants) within two weeks prior to initial IMD injection and to a minimum of four weeks post IMD injections
- 17. Any medical condition which, in the investigator's opinion, prohibits the inclusion in the study
- 18. Current or previous (within 30 days of enrolment) treatment with another investigational drug and/or medical device or participation in another clinical study
- 19. Previous enrolment in this clinical investigation
- 20. Any dependent relationship of the subject with the investigator, investigation site or Sponsor (e.g. employees or relatives)
- 21. Subjects whose participation in clinical trials is prohibited by the Austrian Medical Devices Act (e.g., persons with a legal custodian appointed due to mental disability, prisoners, soldiers and other members of the armed forces, civil servants)

6.3.5 Withdrawal criteria and procedures

The subject may be withdrawn from the investigation for any of the following reasons:

- 1. Occurrence of an AE which requires a premature termination of the treatment or precludes followup of the subject
- 2. A major CIP deviation, which may interfere with evaluation of the treatment outcome (e.g., additional aesthetic correction of the defect during the course of the study, use of prohibited medication, or similar)
- 3. Investigator's decision, triggered by safety, behavioural or administrative reasons
- 4. Pregnancy
- 5. Informed consent withdrawal

A subject is free to withdraw the consent and leave the investigation at any time with no obligation to specify the reason for withdrawal.

Efforts should be made, however, to get in touch with subjects who did not attend the scheduled visit and clarify the reason for default. If the subject is unreachable, a corresponding note should be provided in the subject's medical record.

Reasons, circumstances and findings related to early withdrawal should be fully described in the subject's medical records and the eCRF respecting the subject's rights.

Attempts should be made to perform an early termination visit, which should consist of the assessments planned for the Month 18 visit (Visit 6; also see section 6.5.6). In the event that the withdrawal is caused by an AE, the procedures stated in section 14.6 must be followed.

Depending on the time point of withdrawal, a withdrawn subject is referred to as either "screening/baseline failure" or "dropout" as specified in section 6.3.10.

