6.3.6 Replacement of subjects

Subjects withdrawn from the investigation or lost for follow-up will not be replaced. No re-screening is allowed.

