6.5.6 Early Termination Visit

At Early Termination Visit, or whenever the subject is withdrawn from the clinical investigation, all attempts should be made to perform the assessments described for Visit 6 (see section 6.5.5).

For safety reasons, the following assessments are recommended to be completed at a minimum:

- Record any new AE or changes of AEs (see section 14)
- Record changes in concomitant medication and procedures (see section 6.4.3)
- Lips fullness assessment (LFS) investigator (see section 6.4.7)

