7.2 Analysed data sets

Safety Analysis Set (SAF)

The Safety Analysis Set (SAF) consists of all subjects who received at least one administration of the investigational medical device (IMD).

Full Analysis Set (FAS)

The Full Analysis Set (FAS) comprises all subjects who received at least one administration of the IMD and who had at least one post-treatment evaluation of the LFS.

Per-Protocol Set (PPS):

The Per-Protocol Set (PPS) includes all subjects of the FAS who have no major protocol deviations.

Subjects with major protocol deviations will be excluded from the PPS. For this purpose, protocol deviations that could interfere with the objectives of the study, use of prohibited concomitant medications/procedures or deviation of the inclusion/exclusion criteria etc. will be assessed as 'minor' or 'major' in collaboration with the sponsor in the Data Review Meeting (DRM). The criteria for this assessment will be defined before analysis in the SAP. Listings will be prepared to assess the eligibility of all subjects during the DRM.

All safety analyses will be based on the SAF. The primary data set for effectiveness analysis will be the FAS and PPS. Certain sensitivity analyses may be also done in the PPS.

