7.5 Missing data

Adverse events with unknown onset times will be counted as post IMD administration AEs. AEs with missing relationship to IMD will be counted as related AEs (ADEs).

In addition, there will be no imputation of missing values. All data will be analyzed as they appear in the data base.

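### CIP 6.3.5 permits withdrawal from all follow-up for an additional lip correction, which can overstate late response and lose long-term safety data

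*Protocol*

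**What the plan says.** CIP 6.3.5 opens with "The subject may be withdrawn from the investigation for any of the following reasons". Item 2 of the list is "A major CIP deviation, which may interfere with evaluation of the treatment outcome (e.g., additional aesthetic correction of the defect", and use of prohibited medication is a further example. Item 2 does not say who decides. The investigator's own decision is a separate item 3.

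On leaving: "Attempts should be made to perform an early termination visit, which should consist of the assessments planned for the Month 18 visit". CIP 6.5.6 sets a floor for that visit ("For safety reasons, the following assessments are recommended to be completed at a minimum"): AEs, concomitant medication and procedures, and the investigator's LFS. Nothing is scheduled afterwards. CIP 14.3 documents AEs up to the last visit. CIP 14.6 follows AEs at most to the subject's last day in the investigation, except that device-related SAEs are followed to recovery, death or stability. CIP 6.3.6 adds: "Subjects withdrawn from the investigation or lost for follow-up will not be replaced".

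On analysis, CIP 7.5 states: "In addition, there will be no imputation of missing values". SAP 9.5.1 imputes only FACE-Q items and certain AE and medication fields. SAP 9.5.2 bases summaries on scheduled time points. Neither document assigns an early termination LFS to a scheduled visit, or says how a rating made after a further lip correction enters the Month 6, 12 or 18 rates.

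The text on further injections does not fit together. Inclusion criterion 5 (CIP 6.3.3) has subjects agree to abstain from procedures in the treatment area throughout. CIP 6.3.8 and 6.4.12 mention new injections, generally after three months, once the effect has gone, without saying whether that means during the study. CIP 6.3.5 treats an additional correction as a deviation that may end participation.

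**The concern.** The last study treatment is the optional touch-up at Week 3. A withdrawal after that stops no study treatment; it stops only the collection of data.

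The trigger is plausibly related to outcome. CIP 2.1 and 4.1 anticipate an effect of up to nine months, while follow-up runs to 12 or 18 months. A subject who obtains more filler in that period is likely to be one whose effect has diminished. If such a subject is withdrawn, and the percentages use observed values at scheduled visits, a likely non-responder leaves the denominator. AE collection also ends, including the period after new filler is placed over the study device.

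Duration of effect and long-term safety are both main objectives (CIP 5.1), and both depend on the late visits.

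**Working it through.** **Inputs.** From the documents: 100 evaluable subjects, 10% added for drop-out, and an expected Week 6 response of 0.900 (CIP 7.1, SAP 9.6). Assumed, because the documents give no such figures: the true Month 12 response p, the share w withdrawn after an additional correction, and the response rate q among those withdrawn.

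**1. The plan's precision figure.** 1.96 × √(0.9 × 0.1 / 100) = 0.0588, and with n = 50 it is 0.0832. Both match the stated 0.059 and 0.083. They apply to a 90% rate. For a 60% late rate the half-width is 1.96 × √(0.6 × 0.4 / 100) = 0.096, or 9.6 points.

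**2. Observed-case rate.** Observed = (p − wq)/(1 − w), so the overstatement is w(p − q)/(1 − w).

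With p = 0.60 and q = 0 (all withdrawn subjects are non-responders):
- 5 of 100 withdrawn: 60/95 = 63.2%, +3.2 points.
- 10 of 100 withdrawn: 60/90 = 66.7%, +6.7 points. Ten is the plan's whole drop-out allowance, for all causes.

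**3. Sensitivity to the assumptions.** Overstatement in points, q = 0:

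| True rate p | w = 5% | w = 10% | w = 20% |
|---|---|---|---|
| 30% | 1.6 | 3.3 | 7.5 |
| 50% | 2.6 | 5.6 | 12.5 |
| 70% | 3.7 | 7.8 | 17.5 |

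The half-widths for these observed rates run from about 7 to 11 points. By the formula, the overstatement halves if q = p/2 and is zero if q = p. The 20% column is twice the plan's allowance and should be read as an extreme.

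**4. Retention without an analysis rule.** Suppose the same 10 non-responders stay in follow-up and all are rated improved because of the new filler. The rate becomes (60 + 10)/100 = 70.0%, which is further from 60% than the 66.7% after withdrawal. If they are counted as non-responders from the date of correction, the rate is 60/100 = 60.0%. Continued follow-up and the analysis rule are therefore both needed.

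**5. Late safety.** With no events observed, the 95% upper bound is 1 − 0.05^(1/n): 2.7% for n = 110, 3.3% for n = 90 and 3.7% for n = 80. The loss of precision is modest. The larger loss is that nothing is learned about these subjects after they leave.

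**6. Week 6.** Only a withdrawal before Week 6 could matter. Losing one non-responder per 100 would move 90% to 0.90/0.99 = 90.9%.

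**The case against.** Withdrawal under item 2 is optional, subjects have agreed to abstain, and an exit visit with LFS and AEs is to be attempted. Reasons for withdrawal are recorded and tabulated (CIP 6.3.5, 7.3.3). All of this stands and reduces the expected size. It does not close the gap, because no rule carries the exit LFS into a scheduled-visit rate and general AE collection still ends.

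A second objection is that withdrawal is not the only source of response bias, since ratings after new filler would inflate response too. That is correct (step 4), and it is why the fix includes an analysis rule.

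Several stronger readings are tempting but not supported:
- *Subjects leave because their effect has faded.* The trigger is an additional correction. Loss of effect alone is not a 6.3.5 reason. The option to finish at Month 12 when no effect is visible (CIP 6.4.12) is a separate route.
- *The open-label investigator makes the withdrawal decision.* Item 2 names no decision-maker.
- *The per-protocol exclusion is carried into the FAS.* A subject withdrawn after Week 6 remains in the FAS and contributes every earlier visit. Only the later values are missing.
- *The trigger is unworkable because deviations are graded only later.* CIP 7.2 says deviations "will be assessed as 'minor' or 'major' in collaboration with the sponsor in the Data Review Meeting (DRM"), but for PPS membership. Item 2 has its own test, interference with evaluation of the outcome. The word major has two uses, which is untidy but not unworkable.
- *A false difference between HQ and C1 will appear.* Five withdrawals in one arm only would give 30/45 = 66.7% against 30/50 = 60.0%. The documents give no reason for such one-sidedness, even though the products can be told apart (CIP 6.2.1). The 95% half-width for that difference is 1.96 × √(0.667 × 0.333/45 + 0.6 × 0.4/50), about 19 points.

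**Conclusion.** The point holds as a risk that the plan permits, and the sponsor should address it. Followed as written, the plan can remove likely non-responders from the Month 6, 12 and 18 denominators and end AE collection on them, with no study treatment left to stop.

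A reader might infer that the late rates are biased. The documents do not show that, because they give neither a late response rate nor a re-treatment rate. Under the assumptions used, the overstatement runs from zero, if those withdrawn respond at the average rate, to 17.5 points in the extreme case. For 5 or 10 non-responders lost from a true 60 of 100 it is 3.2 or 6.7 points, inside the half-width of about 9.6 points. The 5.9-point half-width in the plan is not the right yardstick for a 60% rate. The primary endpoint is little exposed.

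**What to change.** 1. **CIP 6.3.5.** State that a deviation, including an additional lip correction, is not by itself a reason to end follow-up. Scheduled visits and AE collection continue, and the deviation and its date are recorded. CIP 6.4.3 already asks at each visit about aesthetic procedures in the treated area.
2. **SAP 10.6.** For the late LFS, GAIS and aesthetic-effect rates in the FAS, do not use ratings made after an additional lip correction. Count the subject as a non-responder at visits from that date, including any subject withdrawn for this reason. Add an observed-case sensitivity analysis.
3. **PPS.** Decide handling by visit, so that valid Week 6 data are kept when the correction came later. SAP 9.2 excludes only subjects whose major deviations affect the primary endpoint, and a correction after the Week 6 visit cannot change that rating.
4. **Reconcile** CIP 6.3.3 (criterion 5), 6.3.5, 6.3.8 and 6.4.12 on further injections during the study. Which clinical rule should apply is for the sponsor and investigators; the changes above concern observation and analysis only.

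The cost is a short CIP amendment, a few SAP sentences, a few more follow-up visits and slightly less favourable late rates. If an amendment comes too late, the SAP rule can still be set before the final database lock.

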6.3.6 Replacement of subjects

Subjects withdrawn from the investigation or lost for follow-up will not be replaced. No re-screening is allowed.

6.3.7 Life-style and other restrictions

Contraception

The safety of Saypha® FILLER Lidocaine administration in pregnancy has not been established. Non-clinical studies on reproductive and developmental toxicity of Saypha® FILLER Lidocaine have *not* been conducted. No studies on the effect of Saypha® FILLER Lidocaine on lactation have been conducted. So women of childbearing potential participation should not be pregnant and should use highly effective contraception or avoid unprotected sexual intercourse throughout the clinical investigation. Any pregnancy occurring in study subjects during the investigation (i.e., from date of ICF signature until the last scheduled visit) should be reported as AE and followed-up as described in section 14.

Note 1: A woman is considered to be of childbearing potential (WOCBP) if fertile, following menarche and until becoming postmenopausal unless permanently sterile. Permanent sterilization methods include hysterectomy, bilateral salpingectomy and bilateral oophorectomy. A postmenopausal state is defined as no menses for 12 months without an alternative medical cause.

Note 2: Highly effective methods of birth control include: combined (estrogen and progestogen containing) hormonal contraception associated with inhibition of ovulation (oral, intravaginal, transdermal), progestogen-only hormonal contraception associated with inhibition of ovulation (oral, injectable, implantable), intrauterine device (IUD), intrauterine hormone-releasing system (IUS), bilateral tubal occlusion), vasectomized partner (provided that is the sole sexual partner of the subject and that the vasectomized partner has received medical assessment of the surgical success.) or sexual abstinence (if in line with the preferred and usual lifestyle of the subject and defined as refraining from heterosexual intercourse during the entire period of the trial.

Other restrictions

The following restrictions apply to all subjects:

- Make-up should not be applied for 12 hours after each IMD injection;
- Prolonged exposure to sunlight or ultraviolet (UV) radiation must be avoided for one week after each IMD injection; lip care with UV protection should be used daily throughout the entire clinical investigation;
- To minimise the risk of product mobility, the subject should be advised to avoid massaging the
 treatment site or applying pressure to this area for one week following each IMD injection
 (exception: a light massage may be applied after injection of the device for uniform distribution of
 the filler by the investigator see section 6.2.2);
- Use of saunas or Turkish baths is prohibited for one week after each IMD injection.
- Beard longer three-day beard, or excessive facial hair that could interfere in evaluation of treatment as judged by the investigator (see ExC#5)

6.3.8 Prohibited medication and aesthetic treatments

The following medications and treatments are prohibited prior to start of the investigation and during the entire investigation, if not stated otherwise below (also refer to the respective ExC in section 6.3.4):

- Prior surgery or tattoo to the upper or lower lip or lip line (see ExC#4)
- Previous tissue augmenting therapy in the lip area (including lips, oral commissures, nasolabial folds, marionette and perioral lines) with HA or collagen filler, or laser treatment, chemical peeling, dermabrasion or mesotherapy within 12 months before Visit 1 (see ExC#7)
- Previous permanent implant or treatment with non-HA or non-collagen filler in the lip area (including lips, oral commissures, nasolabial folds, marionette and perioral lines) (see ExC#8)
- Previous toxin treatment in the lip area (including lips, oral commissures, nasolabial folds, marionette and perioral lines) within 9 months before Visit 1 (see ExC#9)
- History or presence of any autoimmune or connective tissue disease, or current treatment with immune therapy (see ExC#14)
- Anticoagulant, antiplatelet, or thrombolytic drugs (e.g. acetylsalicylic acid) from ten days pre- until three days after each injection of the device (see ExC#16)
- Planned dental/oral surgery or modification (bridge-work, implants) within two weeks prior to initial IMD injection and to a minimum of four weeks post IMD injections (see ExC#17)
- Current or previous (within 30 days of enrolment) treatment with another investigational drug and/or medical device or participation in another clinical study (see ExC#19)
- If no aesthetic effect is present anymore new injections for lip augmentation might be placed after 3 months in general (see section 6.4.12).
- According to IB (see section 8.1.5) sensitive skin may be pre-treated using a local anaesthetic
 patch or cream. However, a pre-treatment with local anaesthetics is not allowed in this
 investigation to not falsify the pain assessment (as collected via Numerical Pain Rating Scale; see
 section 6.4.8).

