6.3.9 Medical care upon termination of the clinical investigation

The study participants will not receive any study-specific treatment after the final visit. Any further treatment, if needed, will be proposed to the subject by the investigator at their discretion.

In case no aesthetic effect is present anymore new injections might be placed at previously injected locations after 3 months in general (see section 6.4.12).

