6.4.3 Prior and concomitant medication and non-drug therapies

Prior medication and procedures (e.g. surgeries or aesthetic procedures) are as all medication taken or procedures performed within ten days (whether continuing or not) prior to Visit 1 (Day 0).

Concomitant medication / procedure is defined as all medication taken or procedures performed from Visit 1 (including medication taken immediately pre-injection and post-injection of the IMD) until the final visit (Visit 5 or 6, if applicable).

At each visit the subject will be asked about any new medication taken or changes in current medication, as well as about any aesthetic procedure applied in the area treated with the IMD.

Prior and concomitant medication and non-pharmacological procedure applied (e.g. surgeries or aesthetic procedures) will be documented in the subject's medical record and in the eCRF classified by drug generic name / trade name or active substance (in case that no generic name is available).

Prohibited concomitant medications and non-pharmacological procedure (e.g. surgeries or aesthetic procedures) are listed in section 6.3.7.

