6.4.12 Assessment of aesthetic effect

At each follow-up visit, the investigator will evaluate the aesthetic effect. The presence of an aesthetic effect at a given visit relative to baseline will be recorded as either "YES" or "NO" in the subject's medical record and in the eCRF.

The duration of the clinical investigation is planned for 18 months at a maximum and depends on the assessment of the aesthetic effect. In case it is observed by the investigator that no aesthetic effect is any more visible the study can be terminated at Month 12 (Visit 5) for the respective subject.

If no aesthetic effect is present anymore new injections for lip augmentation might be placed at previously injected locations after 3 months in general.

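### CIP 6.3.8 and 6.4.12 do not limit lip re-injection to after study exit, and the SAP has no re-treatment rule, so a re-injected subject who stays in could count as a late responder

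*Protocol*

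**What the plan says.** CIP 6.3.8 bars the listed medications and treatments before and throughout the investigation, unless an item in the list says otherwise. One item reads: "If no aesthetic effect is present anymore new injections for lip augmentation might be placed after 3 months in general". CIP 6.4.12, on the follow-up assessment of aesthetic effect, says that once the effect has gone "new injections for lip augmentation might be placed at previously injected locations after 3 months in general". Neither section adds that the subject must first have left the study. CIP 6.3.9, on care at the end of the investigation, carries nearly the same sentence: "In case no aesthetic effect is present anymore new injections might be placed at previously injected locations after 3 months in general".

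Other parts of the CIP forbid re-injection during the study:

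- Inclusion criterion 5 (CIP 6.3.3) requires "Willingness to abstain from any cosmetic or surgical procedures in the treatment area for the duration of the clinical investigation".
- The CIP 6.3.4 exclusion that covers HA and collagen filler in the lip area ends with "dermabrasion or mesotherapy within 12 months before Visit 1 and until end of clinical investigation".
- CIP 6.3.5 gives "additional aesthetic correction of the defect during the course of the study" as an example of a major deviation, in a list that opens "The subject may be withdrawn from the investigation for any of the following reasons".

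A re-injection would be recorded. CIP 6.4.3 has the subject asked at each visit about medication changes "as well as about any aesthetic procedure applied in the area treated with the IMD".

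On the analysis side, the FAS (SAP 9.2) needs one administration and one post-treatment Lip Fullness Scale (LFS) evaluation. SAP 8.2.1 judges response at each visit against the pre-treatment baseline. SAP 10.6.2 summarises the late endpoints in the FAS and the per-protocol set (PPS). The SAP does not mention re-treatment.

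**The concern.** Duration of the aesthetic effect is a main objective (CIP 5.1, SAP 7.1.1). The re-injection sentence applies to subjects who have lost the effect, so these are the subjects whose late scores should show that loss. LFS response, the Global Aesthetic Improvement Scale (GAIS) and the yes/no aesthetic-effect item are all judged against the state before the first treatment. A newly refilled lip can therefore score as a success on all three, and the result would be credited to the initial injection.

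The late percentages could then overstate duration. The manufacturing-site comparison is more sensitive, because its groups are half the size and SAP 10.8 runs it in the FAS only. The one sensitivity analysis in SAP 10.9 looks at site effect on the primary endpoint and would not reveal this.

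**Working it through.** **1. Where a re-injected subject would end up.**

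- *Staying in.* CIP 6.3.5 makes withdrawal possible, not mandatory. Exit for lost effect is offered only at Month 12 (CIP 6.4.12, 6.5.5).
- *FAS.* Nothing in the definition removes the subject or the later visits.
- *PPS.* SAP 9.2 and 9.4 send prohibited procedures, and deviations that could interfere with the study objectives, to grading at the Data Review Meeting. SAP 9.2 then excludes only major deviations that affect the primary endpoint. SAP 9.4 says subjects with major deviations are excluded, but also lets some of them stay. The primary endpoint is at Week 6, so a later re-injection cannot change it. The grading could go either way.

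**2. Which visits are exposed.**

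- *Week 6:* not exposed.
- *Month 6:* narrowly exposed. The effect must be lost and the 3 months (no starting point is given) must have passed before Week 26, against an anticipated lifetime of up to nine months (CIP 2.1).
- *Month 12:* the main exposure, because loss of effect before then is foreseeable.
- *Month 18:* also exposed. CIP 6.5.5 schedules Visit 6 unless no effect is visible at Month 12. A subject re-injected before Month 12 would show one and be scheduled.

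**3. The plan's own precision figures.** Inputs from CIP 7.1 and SAP 9.6: p = 0.90, n = 100 overall and 50 per manufacturing site, two-sided 95%. Half-width = 1.96 × √(p(1−p)/n).

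- n = 100: 1.96 × √(0.09/100) = 0.0588, stated as 0.059.
- n = 50: 1.96 × √(0.09/50) = 0.0832, stated as 0.083.

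Both reproduce.

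**4. Shift per re-injected subject.** Shift in points = 100 × k × f / n. Here k is the number of re-injected subjects counted as responders, and f is the share of them who would otherwise be non-responders. A subject can lose the visible effect and still be one LFS grade above baseline, so f may be below 1. I assume f from 0.5 to 1.0.

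| k | n = 100 | n = 50 |
|---|---|---|
| 1 | 0.5 to 1.0 | 1.0 to 2.0 |
| 5 | 2.5 to 5.0 | 5.0 to 10.0 |

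Month 18 is optional, so its denominator is probably smaller and each subject would weigh more there.

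**5. How much the rule matters.** Illustration at Month 12 with an assumed 50% counted rate and k = 5:

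| Rule | n = 100 | n = 50 |
|---|---|---|
| Counted as recorded | 50/100 = 50.0% | 25/50 = 50.0% |
| Subject excluded | 45/95 = 47.4% | 20/45 = 44.4% |
| Counted as non-responder | 45/100 = 45.0% | 20/50 = 40.0% |

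**6. Scale against sampling error.** At p = 0.5 the half-width is 1.96 × √(0.25/100) = 9.8 points for n = 100 and 1.96 × √(0.25/50) = 13.9 points for n = 50. To move the rate by one half-width takes:

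- n = 100: 9.8 subjects at f = 1, or 19.6 at f = 0.5, so about 10 to 20.
- n = 50: 6.9 subjects at f = 1, or 13.9 at f = 0.5, so about 7 to 14.

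**The case against.** The strongest reply is that the CIP, read as a whole, forbids re-injection during the study. The inclusion, exclusion and withdrawal texts all say so. In 6.4.12 the sentence comes straight after the text on ending participation at Month 12, and 6.3.9 places it under care after termination. The schedule has injections only at Day 0 and, optionally, Week 3. Supply fits this: CIP 6.2.7 plans up to 440 units of 1 mL for 110 subjects, and 440/110 = 4 mL each, which is 2 mL for the initial treatment plus 2 mL for the touch-up. Nothing is left for a later injection.

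Most of this stands. A reader might infer from 6.3.8 alone that the CIP openly permits in-study re-injection, and the documents do not support that. What they show is a contradiction whose likely intent is post-exit care. Likely intent does not remove the contradiction: 6.3.8 allows exceptions within its own list, and an investigator who reads only 6.3.8 or 6.4.12 could re-inject in good faith.

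Three further inferences also go too far:

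- CIP 7.5, on analysing data as they stand in the database, might be read as an instruction to keep scores after re-injection. It is a missing-data statement that follows the ban on imputation. The argument here rests on the FAS definition and the baseline comparison.
- The permissive verb in 6.3.5 might be read as a plan to keep re-injected subjects. It introduces every listed reason, including pregnancy and withdrawn consent, so it shows only that withdrawal is not guaranteed.
- The PPS might be said certainly to retain these subjects. The Data Review Meeting could exclude them: 6.3.5 names the event as a major deviation, SAP 9.4 also counts indirect influence such as major GCP deviations, and CIP section 10 has evaluability discussed. The outcome is unsettled, not fixed.

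**Conclusion.** The point holds as an internal contradiction in the CIP combined with a gap in the SAP. If a subject is re-injected and not withdrawn, the FAS would count the later scores as response to the initial treatment, and the PPS may or may not remove them.

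Any resulting bias in the late LFS, GAIS and aesthetic-effect rates is upward. The ceiling is 1 point per re-injected subject at n = 100, or 2 points at n = 50. It is lower if some would have been LFS responders anyway. Month 12 is the main exposure, with carry-over into Month 18.

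The likely size is small. The documents give no re-injection rate; the 50% rate, k = 5 and the range for f are assumptions. A reader might infer that the duration results are seriously compromised, but a shift of one full half-width would need about 10 to 20 of 100 subjects, and nothing in the documents suggests that many. The Week 6 primary endpoint and the sample size are unaffected. Low to moderate priority.

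**What to change.** In CIP 6.3.8 and 6.4.12, add *only after study exit* to the sentence, in line with 6.3.9.

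In the SAP, before database lock, state two things:

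- From the date of any further lip filler, a subject counts as a non-responder, or as having no effect, for later LFS, GAIS and aesthetic-effect endpoints in both FAS and PPS. FACE-Q scores from those visits are left out of the summaries.
- A sensitivity analysis excludes those visits. If exclusion is preferred as the main rule, fix that before lock and report the non-responder rule as the sensitivity analysis.

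Cost: a short written CIP amendment, signed by sponsor and investigator and sent for ethics review if CIP section 9 requires it, plus two SAP sentences. The data needed are already collected under CIP 6.4.3. Late responder rates may be slightly lower.
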